6.3.3. Biomicroscopy Findings

Slit lamp biomicroscopy assessments will be performed using the ISO11980 grading at the Screening/Baseline visit (Day 1) and at Visit 3 (and at unscheduled and early exit visits, as necessary).

Biomicroscopy parameters will be summarized [eye-level summary] using descriptive statistics by analysis visit:

- Limbal Hyperemia: None, Trace, Mild, Moderate and Severe.
- Bulbar Hyperemia: None, Trace, Mild, Moderate and Severe.
- Corneal Epithelial Edema: None, Trace, Mild, Moderate and Severe.
- Corneal Stromal Edema (only Group 2): None, Trace, Mild, Moderate and Severe.
- Corneal Vascularization: None, Trace, Mild, Moderate and Severe.
- Conjunctival Compression/Indentation (only Group 2): Absent, Present.
- Chemosis: Absent, Present.
- Corneal Infiltrates (only Group 2): None, Trace, Mild, Moderate and Severe.
 - Central: Yes, No.
 - Peripheral Superior: Yes, No.
 - Peripheral Inferior: Yes, No.
 - Peripheral Nasal: Yes, No.
 - Peripheral Temporal: Yes, No.
 - Type: Focal, Diffuse.
 - Depth of Largest Infiltrate: Epithelial, Anterior stromal, Mid/posterior stromal.
 - Number of Infiltrates: 1, 2, 3, 4, 5, 6, 7, ≥ 8 .
 - Size of the Largest Infiltrate (mm).
- Corneal Staining: Absent, Present.
 - Central: None, Trace, Mild, Moderate and Severe.

- Superior: None, Trace, Mild, Moderate and Severe.
- Nasal: None, Trace, Mild, Moderate and Severe.
- Inferior: None, Trace, Mild, Moderate and Severe.
- Temporal: None, Trace, Mild, Moderate and Severe.
- Conjunctival Staining: None, Trace, Mild, Moderate and Severe.
- Palpebral Conjunctival Observations: None, Trace, Mild, Moderate and Severe.
- Other Findings: None, Trace, Mild, Moderate and Severe.

Shift tables will be generated using the ISO11980 grading categories. The number and percentage of eyes shifting from categories between Baseline and Visit 3 will be summarized.

A supportive listing for biomicroscopy assessments will be provided.

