7.3.4.2 Slit Lamp Biomicroscopy

Slit lamp biomicroscopy assessments will be performed using the ISO11980 grading at the Screening/Baseline visit (D1) and at Visit 3 (and at unscheduled and early exit visits, as necessary).

A biomicroscopy examination of the cornea, adnexa and anterior segment of the eye will be performed, OD and OS, at the Screening/Baseline visit (D1) and at Visit 3 (and at unscheduled and early exit visits, as necessary), and recorded on eCRFs. Record both eyes for the same subject if both are noted to have such a finding.

If warranted, a short slit lamp video or slit lamp photograph should be recorded to demonstrate any abnormal findings or findings of interest during biomicroscopy (for example inferior arcuate staining). Record both eyes for the same subject if both are noted to have such a finding.

- Limbal hyperemia (All Subjects)

Limbal hyperemia (redness) will be recorded on a 5-point scale as follows:

0 = None	No hyperemia
1 = Trace	Slight limbal hyperemia (mild segmented)
2 = Mild	Mild limbal hyperemia (mild circumcorneal)
3 = Moderate	Significant limbal hyperemia (marked segmented)
4 = Severe	Severe limbal hyperemia (marked circumcorneal)

- Bulbar Hyperemia (All Subjects)

Bulbar conjunctival hyperemia (redness) will be recorded on a 5-point scale as follows:

0 = None	No hyperemia
1 = Trace	Slight regional hyperemia
2 = Mild	Diffuse hyperemia
3 = Moderate	Marked regional or diffuse hyperemia
4 = Severe	Diffuse episcleral or scleral hyperemia

- Corneal Epithelial Edema (All Subjects)

Corneal epithelial edema should be classified according to the number of microcysts observed. The presence/absence of fluid-filled or debris-filled cysts should be documented.

0 = None	No microcysts; normal transparency
1 = Trace	1 to 20 microcysts; barely discernable local epithelial haziness
2 = Mild	21 to 50 microcysts; faint but definite localized or generalized haziness
3 = Moderate	51 to 100 microcysts; significant localized or generalized haziness
4 = Severe	> 100 microcysts; definite widespread epithelial cloudiness giving a dull glass appearance to the cornea or numerous coalescing bullae

- Corneal Stromal Edema (Group 2)

Corneal stromal edema will be recorded on a 5-point scale as follows:

0 = None	No edema
1 = Trace	Just detectable clouding
2 = Mild	Faint corneal striae (2 or fewer)

3 = Moderate	Pronounced corneal striae (3)
4 = Severe	Folds in descemet's membrane and ≥ 4 pronounced striae

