Ask the subject to look up and nasally. Gently retract the lower lid and touch the strip to the inferior temporal bulbar conjunctiva, approximately 5 mm or more from the limbus, for 1 to 2 seconds, so that 1 to 2 mm of the flat side of the strip makes contact with the ocular surface. Withdraw the strip and release the lower lid.

[figure not shown]
- Corneal Staining - Standard Assessment

Record grade according to the following scale:

0 = None	No staining
1 = Trace	Minimal superficial staining or punctate staining a) Dimpling, discrete dot staining, or b) Trace superficial lens insertion marks or foreign body tracks
2 = Mild	Regional or diffuse punctate staining a) Central or generalized, or b) Peripheral including 3 to 9 o'clock staining, or c) Foreign body tracks
3 = Moderate	Dense coalescent staining up to 2 mm in diameter a) Corneal abrasion b) Foreign body track
4 = Severe	Dense coalescent staining greater than 2 mm in diameter

The location of staining observed should be recorded in source documentation only, as indicated in Figure 2:

Figure 2. Corneal Regions for Recording Location

Recurrent erosion and corneal ulceration should be recorded under “Other findings.”

Inferior arcuate staining should be recorded under “Other findings.”

- **Conjunctival Staining (All Subjects)**

Conjunctival staining should be assessed immediately after corneal staining. Therefore, an additional application of NaFl is not required. However, if needed in order to make a sound judgment, one more application can be made following the instructions given in the section above and using a new NaFl strip. All conjunctival staining observations should be carried out using a blue excitation light in conjunction with a yellow barrier filter in the observation system after NaFl instillation.

Conjunctival staining will be assessed on a 5-point scale:

0 = None	No staining
1 = Trace	Minimal regional staining
2 = Mild	Regional or diffuse punctate staining
3 = Moderate	Significant dense coalescent staining
4 = Severe	Severe dense geographical staining

- **Palpebral conjunctival observations (All Subjects)**

The severity of the maximal palpebral conjunctival response will be recorded on a 5-point scale as follows:

0 = None	Uniform satin appearance of the conjunctiva
1 = Trace	Slight conjunctival injection without texture
2 = Mild	Mild or scattered papillae/follicles less than 1 mm in diameter

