3 = Moderate	Significant papillae/follicles less than 1 mm in diameter, and/or marked conjunctival injection Staining of the top of one papilla
4 = Severe	Localized or generalized papillae/follicles 1 mm or more in diameter Staining of the top of more than one papilla

- Other Findings (All Subjects)

Record any other finding(s) and use the following scale to grade severity:

0 = None	No other significant biomicroscopic findings
1 = Trace	Minimal findings
2 = Mild	Mild findings
3 = Moderate	Significant findings
4 = Severe	Severe findings

Note: If there are multiple other findings, on the eCRF for “Other” record the grade of the most severe in the “Result” field and record all findings (along with their individual grades) in the “If Other, Specify” field.

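### Does the mismatch between the SAP's corneal staining rows and the protocol's 0-4 staining grade call for a change to the plan?

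*SAP*

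**What the plan says.** Protocol 7.3.4.2 has the slit lamp examination done separately in each eye ("anterior segment of the eye will be performed, OD and OS"). For corneal staining it says "Record grade according to the following scale" and sets out five levels, from 0 (none) to 4 (severe). On location it adds: "The location of staining observed should be recorded in source documentation only".

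SAP 6.3.3 summarises the parameter by analysis visit as "Corneal Staining: Absent, Present", followed by five regional rows (central, superior, nasal, inferior, temporal). Each is graded in the form "Superior: None, Trace, Mild, Moderate and Severe". The section then says "Shift tables will be generated using the ISO11980 grading categories".

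SAP 13 gives staining its own by-visit summary (Table 14.3.3.3), shift table (Table 14.3.3.4) and listing (Listing 16.2.6.2.2). It notes that the shells are held in a separate document.

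**The concern.** Corneal staining is the one biomicroscopy finding that the safety endpoint names, and the SAP appears to summarise something other than what the protocol collects. There is no row for the protocol's grade, and no rule for turning regional grades into a whole-eye grade or into presence. The SAP text does not say which staining variable Table 14.3.3.4 uses.

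The protocol does give a worst-case rule for two other parameters: "The severity of the maximal palpebral conjunctival response will be recorded on a 5-point scale", and for multiple other findings "record the grade of the most severe". It gives none for staining.

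If only one grade per eye were in the database, the regional rows would be empty and the by-visit table would show presence or absence alone. A move from trace to severe staining would not appear in that table.

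**Working it through.** The plan states no figure on this point. Its one calculation is the precision of an adverse event rate, 1.96 × √(0.0543 × 0.9457 / 54) = 0.0604. That agrees with the stated 0.060 and plays no part here. The check is a comparison of the two texts.

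1. **Is the mismatch real?** Protocol 7.3.4.2 grades ten parameters 0-4: limbal hyperemia, bulbar hyperemia, epithelial edema, stromal edema, vascularization, infiltrates, corneal staining, conjunctival staining, palpebral response and other findings. SAP 6.3.3 has an overall graded row for nine of them; corneal staining is the exception. For infiltrates the protocol describes a form with location fields, and the SAP's location rows match that form. No such form is described for staining. The mismatch is real.

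2. **Could the regional rows be derived from one grade?** No. Suppose the single grade is that of the worst region. The number of five-region patterns with worst grade g is (g+1)⁵ − g⁵. For g = 0 to 4 this gives 1, 31, 211, 781 and 2101, which sum to 5⁵ = 3125. Apart from grade 0, a single grade does not identify the regional pattern.

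3. **What follows under each form of data capture?**

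| Database holds | SAP rows that can be filled | What remains |
|---|---|---|
| One grade per eye | 1 of 6 (presence or absence) | 5 regional rows × 2 visits = 10 summaries without a source |
| Regional grades | 6 of 6 | Protocol location sentence out of date |
| Both | 6 of 6 | As above, and no by-visit row for the overall grade |

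The documents do not say which line applies. One grade per eye is the more natural reading of the protocol, because its grade 2 covers both central and generalized staining. The protocol does not use the word single or overall, however. The separate staining table and listing in SAP 13 would fit a dedicated eCRF page with regional fields.

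4. **Is a rule for presence missing?** Not in substance. Grade 0 is defined as no staining. An eye is therefore absent if its grade is 0 or all its regional grades are 0, and present otherwise.

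5. **Is severity lost in the worst case?** With one grade per eye, that grade is the only graded staining variable, so the shift table must use it. The row and column totals of a Baseline to Visit 3 shift table give the five-level distribution at both visits for eyes with paired data. The listing covers the remaining eyes. With regional grades, severity is already in the by-visit rows. Separately, Protocol 9.2 has any clinically relevant worsening of a study parameter, in the investigator's opinion, reported as an adverse event.

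**The case for a change.** The best case for a change is that something in the documents is wrong under either form of capture. With one grade, most of the staining rows in SAP 6.3.3 have no source. With regional grades, the protocol's restriction of location to source documents is contradicted, and the SAP does not name the variable behind Table 14.3.3.4. The study is open-label, so derivations are best fixed before lock, and a check of one eCRF page costs little.

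The inconsistency stands, and so does the unnamed shift variable. The consequence does not. The count of five rows in six holds only under one form of capture, which the documents do not establish. A worst-region grade for the whole eye is one reasonable summary; reporting by region is another. The worst-case rules for palpebral and other findings apply to those parameters, and the lack of one for staining contradicts nothing.

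The open-label argument carries little weight because SAP 6.2 formulates no safety hypotheses and draws no inferences. Any correction would also have to begin with the eCRF and shells, which may already settle the layout.

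**Conclusion.** The protocol and SAP describe corneal staining differently, but no change to the plan follows. The programmer will see from the database which form was captured. If there is one grade per eye, the regional rows are dropped and the grade is tabulated. SAP 1.1 allows a small departure of that kind from the planned analyses to be recorded with its rationale in the study report. If there are regional grades, the SAP can be run as written and what remains is a clerical slip in one protocol sentence. SAP 1.1 does not cover that slip, since it concerns departures from SAP analyses, but correcting the sentence would alter no output.

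The most that can go wrong is 10 row-by-visit summaries that cannot be filled in one descriptive safety table. Primary endpoints, adverse event analyses and sample size are untouched.

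This rests on two assumptions: that the grading categories named for the shift tables are the protocol's 0-4 levels, and that the staining listing shows the recorded grades. Both are the ordinary reading, but the shells and eCRF were not available to confirm them.

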6 STUDY DESIGN

6.1 Overview of Study Design

This is a post-market, multicenter, non-comparative, open-label, prospective clinical study.

The study will be conducted outside the US, where the Systane Ultra PF is commercially available, in clinical sites known to routinely manage subjects with DED and CL wearers. The overall study duration (first subject screened to last subject's final study visit) is expected to be approximately 2 months.

Subjects will be enrolled into the study after signing the informed consent form (ICF).

Subjects who meet all the inclusion criteria and none of the exclusion criteria will initiate treatment with Systane Ultra PF. Eligible study participants (Group 1 and Group 2) will receive the first dose of Systane Ultra PF at the Screening/Baseline visit and will be required to self-administer Systane Ultra PF four times daily up to Visit 3. The dose selected in this study is the dose approved for Systane Ultra PF for the management of DED.

[figure not shown]
Subjects will participate in the study for approximately 30 days, with a phone call scheduled on Day 15 ± 2 (Visit 2) and a follow-up visit scheduled on Day 30 ± 2 (Visit 3). Subjects may have unscheduled visits if deemed necessary per the Investigator's judgment.

Subjects will be asked to complete patient questionnaires on Day 1 and at Visit 3 (Impact of Dry Eye on Everyday Life - Symptom Bother [IDEEL-SB] or Contact Lens Dry Eye Questionnaire [CLDEQ-8] and Comfortable Wear Time questions). In addition, the subjects will be instructed to document Systane Ultra PF dosing information on a daily basis using a subject diary.

A summary of the study design is shown in Figure 1. Study assessments are shown in the Schedule of Assessments (Table 4).

The study will enroll 68 subjects with the objective of 54 subjects completing treatment (27 in Group 1 and 27 in Group 2).

Figure 1. Overall Study Design

CL: Contact lens; QID: Four times a day.

Systane Ultra Preservative-free will be dispensed at Screening/Baseline visit. Subjects will be expected to attend one additional visit at Day 30 (± 2 days) after screening and a telephone call visit at Day 15 (± 2 days).

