3.5. Analysis Visit Windows

As per the protocol, data will be collected for the assessments at the Screening/Baseline (Visit 1), 15-day Follow-up (Visit 2), and 30-day/Exit (Visit 3). The data will be collected within ± 2 days window for the Visit 2 and Visit 3. By-visit summaries will use the analysis visit. Scheduled, unscheduled and early termination visits will be windowed based on the following analysis visit window ([Table 2](#)).

- 1) If the scheduled records do not fall within a visit window, then the records will be flagged as out of the allowed window and the original visit from the eCRF will be assigned for the analysis visit. In case of unscheduled records not falling within a visit window, the original visit from the eCRF will be assigned.
- 2) For post-baseline visits, if there is more than 1 record available within the same visit window, the following rules will be applied:
 - a. Select the record collected at the scheduled visit.
 - b. If there are no records at the scheduled visit, then the record closest to the target day will be used.
 - c. If there are multiple records with the same distance to the target day, the latest record will be used.
- 3) For Baseline visit, the last non-missing record among scheduled and unscheduled assessments will be selected.

Table 2: Analysis Visit Window

Analysis Visit	Target Study Day	Visit Window for IDEEL-SB, CLDEQ-8, [REDACTED] [REDACTED] BCVA, [REDACTED] Biomicroscopy
Baseline	1	≤ 1
Visit 2	15	13 to 17
Visit 3	30	28 to 32

In general, only observations assigned to an analysis visit window will be included in the analysis. Data collected at unscheduled visits will be included in the data listings. In addition, any data collected out of the allowed window will be flagged in the listings.

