Table 14.1.3.1.1: Summary of Demographics and Baseline Clinical Characteristics – FAS

Table 14.1.3.1.2: Summary of Demographics and Baseline Clinical Characteristics by Site – FAS

Table 14.1.4.1: Summary of Treatment Duration and Missed Doses – FAS

Table 14.2.1.1.1.1: Summary of IDEEL-SB Score by Analysis Visit (Group 1) – FAS

Table 14.2.1.1.1.2: Summary of IDEEL-SB Score by Analysis Visit (Group 1) – PP

Table 14.2.1.2.1.1: Summary of CLDEQ-8 Score by Analysis Visit (Group 2) – FAS

Table 14.2.1.2.1.2: Summary of CLDEQ-8 Score by Analysis Visit (Group 2) – PP

Table 14.3.1.1: Overall Summary of Non-Ocular Treatment-Emergent Adverse Events (TEAEs) - FAS

Table 14.3.1.2.1: Summary of Non-Ocular Treatment-Emergent Adverse Events (TEAEs) by MedDRA PT – FAS

Table 14.3.1.2.2: Summary of Serious Non-Ocular Treatment-Emergent Adverse Events (TEAEs) by MedDRA PT – FAS

Table 14.3.1.2.3: Summary of Non-Ocular Treatment-Emergent Adverse Events (TEAEs) Related with Study Device by MedDRA PT – FAS

Table 14.3.1.3: Overall Summary of Ocular Treatment-Emergent Adverse Events (TEAEs) - FAS

Table 14.3.1.4.1: Summary of Ocular Treatment-Emergent Adverse Events (TEAEs) by MedDRA PT – FAS

Table 14.3.1.4.2: Summary of Serious Ocular Treatment-Emergent Adverse Events (TEAEs) by MedDRA PT – FAS

Table 14.3.1.4.3: Summary of Ocular Treatment-Emergent Adverse Events (TEAEs) Related with Study Device by MedDRA PT – FAS

Table 14.3.2.1: Summary of BCVA Score (logMAR) by Analysis Visit – FAS

Table 14.3.3.1: Summary of Biomicroscopy Findings by Analysis Visit – FAS

Table 14.3.3.2: Shift from Baseline to Visit 3 Biomicroscopy Findings – FAS

Table 14.3.3.3: Summary of Corneal Staining by Analysis Visit – FAS

Table 14.3.3.4: Shift from Baseline to Visit 3 Corneal Staining – FAS

Table 14.3.3.5: Summary of Corneal Infiltrates by Analysis Visit (Group 2) – FAS

Table 14.3.4.1: Summary of Device Deficiencies - FAS

Listing 16.2.1.1: Listing of Subject Disposition

Listing 16.2.1.2: Listing of Missed Visits – FAS

Listing 16.2.2.1: Listing of Protocol Deviations – FAS

Listing 16.2.3.1: Listing of Demographics and Baseline Clinical Characteristics – FAS

Listing 16.2.3.2: Listing of Medical History and Concomitant Medication – FAS

Listing 16.2.3.3: Listing of Missed Doses - FAS

Listing 16.2.4.1: Listing of IDEEL-SB Questionnaire (Group 1) – FAS

■■■■■
Listing 16.2.4.3: Listing of CLDEQ-8 Questionnaire (Group 2) – FAS

■■■■■

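### The biomicroscopy and corneal staining shift tables cannot show a worse grade recorded at an unscheduled examination before day 28 or at an early exit before day 28

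*SAP*

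**What the plan says.** Biomicroscopy, including corneal staining, is a named safety endpoint (Protocol 6.3.3, SAP 6.1). The schedules in both documents place the slit-lamp examination at Day 1 and Visit 3, and at unscheduled or early-exit visits as necessary. Visit 2 is a telephone contact. On unscheduled visits Protocol 6.1 says "Subjects may have unscheduled visits if deemed necessary per the Investigator's judgment".

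For the shift tables, SAP 6.3.3 says "The number and percentage of eyes shifting from categories between Baseline and Visit 3 will be summarized". The output list in SAP Section 13 matches: "Table 14.3.3.2: Shift from Baseline to Visit 3 Biomicroscopy Findings – FAS", with Table 14.3.3.4 doing the same for corneal staining. No worst-grade or maximum-shift output is listed.

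SAP 3.5 decides which record represents a visit. The post-baseline windows are days 13 to 17 (Visit 2) and 28 to 32 (Visit 3). When a window holds several records, the first rule is "Select the record collected at the scheduled visit". The next is "If there are no records at the scheduled visit, then the record closest to the target day will be used", and ties go to the latest record. Grade plays no part. For records outside every window: "In case of unscheduled records not falling within a visit window, the original visit from the eCRF will be assigned". The section ends with "In general, only observations assigned to an analysis visit window will be included in the analysis" and "Data collected at unscheduled visits will be included in the data listings".

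SAP 3.1 is looser. It permits, without committing to it, the use of unscheduled biomicroscopy data in by-visit summaries.

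**The concern.** For a safety sign, a shift table should show how bad an eye became on treatment. Here it shows only how the eye looked at the end. Every slit-lamp record between Day 1 and the Visit 3 window comes from an unscheduled or early-exit visit, and these are the records the shift tables omit.

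Two kinds of eye are affected. An eye with a raised grade on, say, day 10 that is back to its baseline grade at Visit 3 is tabulated as no shift. An eye of a subject who leaves before day 28 has no Visit 3 value and drops out of the table, although Protocol 6.4.6 asks sites to make every effort to complete the early-exit assessments. The shift tables therefore describe eyes that stayed to Visit 3, in their condition at that visit.

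**Working it through.** **The plan's own figure.** The only precision statement (SAP Section 8) is a half-width of 0.060 for an adverse event proportion of 0.0543 with n = 54. It reproduces: 1.96 × √(0.0543 × 0.9457 / 54) = 0.0604. This point does not depend on it.

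**Step 1: which days can reach the shift table.** Inputs are the windows in SAP 3.5, Table 2. Post-baseline days 2 to 32 number 31.

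| Study days | Number of days | Analysis visit | Can an unscheduled examination enter the Baseline-to-Visit 3 shift? |
|---|---|---|---|
| 2–12 and 18–27 | 11 + 10 = 21 | none; keeps its eCRF visit label | No |
| 13–17 | 5 | Visit 2 | No |
| 28–32 | 5 | Visit 3 | Only if there is no scheduled Visit 3 record |

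An unscheduled examination is therefore ineligible on 21 + 5 = 26 of 31 days (83.9%). On the other 5 days (16.1%) it is used only as a fallback. These are shares of calendar days; they do not estimate how often findings occur.

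**Step 2: how a record is lost.** On days 2 to 27 the record is left out because of its date. The preference for the scheduled record operates only within a window, so for the shift table it matters only on days 28 to 32. There the scheduled record displaces an unscheduled one even when the unscheduled grade is worse.

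**Step 3: early exits.** SAP 3.5 applies its windows to early-termination visits too, and no rule carries an examination before day 28 forward to Visit 3. SAP 3.2 bases change summaries on eyes with both a baseline value and a value at the visit summarised. An eye examined at exit on day 20 has the first but not the second, so it is absent from the shift table.

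**Step 4: illustration.** The documents give no rate of transient slit-lamp findings, so the number of affected eyes is assumed. The denominator is 54 evaluable subjects × 2 eyes = 108. Intervals are Clopper-Pearson, the SAP's method for proportions: lower limit Beta(0.025; x, n − x + 1), upper limit Beta(0.975; x + 1, n − x). All affected eyes are assumed to have been examined at an unscheduled visit and to have recovered by Visit 3, with no other eye worse.

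| Eyes affected (assumed) | Worst-grade table | Planned shift table |
|---|---|---|
| 1 of 108 | 0.9% (0.0–5.1) | 0/108 (0–3.4) |
| 3 of 108 | 2.8% (0.6–7.9) | 0/108 (0–3.4) |
| 5 of 108 | 4.6% (1.5–10.5) | 0/108 (0–3.4) |

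The intervals treat fellow eyes as independent.

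**The case against.** The strongest reply is that the plan already reports these findings by other routes.

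- Protocol 9.2 requires a clinically relevant untoward change in a study parameter to be reported as an adverse event regardless of causality. SAP 6.3.1 tabulates ocular events by eye with 95% CIs, including moderate, severe, serious, device-related and discontinuation categories.
- Discontinuations are summarised with reasons (SAP 4.1), and biomicroscopy, corneal staining and infiltrates are listed.
- A record on days 13 to 17 is windowed to Visit 2 and may appear in a by-visit row.
- With one planned post-baseline examination, a worst-grade table will equal the Visit 3 table for most eyes. The study is small and descriptive, and the table shells are in a separate document.

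Much of this stands. It limits the point to the shift tables but does not remove it. The adverse event route depends on the investigator's opinion. Adverse event severity is defined in Protocol 9.3 by tolerance and interference with activities, so it does not convey a slit-lamp grade. Listings give no counts or percentages.

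A reader might infer more than the documents support:

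- **That the worst on-treatment finding is usually seen at an unscheduled visit.** Nothing says so; such examinations are only as necessary, and any worsening present at Visit 3 is tabulated.
- **That the preference for the scheduled record explains a lost day 10 finding.** It does not; that record lies in no window.
- **That a subject who left because of a finding disappears from the report.** Only the shift table loses that subject.
- **That the planned 5.43% indicates the size of the loss.** It is an expected adverse event proportion, not a slit-lamp rate, and events of that kind would appear in the adverse event tables.

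**Conclusion.** The point holds for the shift tables. As planned, they cannot show a worse grade from an unscheduled examination on days 2 to 27 or from an early exit before day 28. On days 28 to 32 they ignore an unscheduled record when a scheduled Visit 3 record exists. This is a gap in descriptive reporting of a named safety endpoint. It does not affect the effectiveness summaries, the sample size or any test, since none is planned.

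The size is unknown. It depends on how many interim examinations take place, how many show a worse grade, and how many of those eyes recover or leave before Visit 3. The 3 of 108 figure is an assumption chosen to show scale. The conclusion on early exits also assumes that an early-exit record keeps its own eCRF label and is not entered as Visit 3. The SAP's rule for out-of-window records names scheduled and unscheduled records but not early-termination ones.

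This is a cheap improvement worth making, not a flaw that undermines the study.

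**What to change.** Before database lock:

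1. In SAP 6.3.3, add a shift from Baseline to the worst post-baseline grade, per eye and per subject (worse eye). Use every scheduled, unscheduled and early-exit examination, and do this for both biomicroscopy and corneal staining.
2. State that this shift is exempt from the window and record-selection rules of SAP 3.5. Lifting only the preference for scheduled records would not recover findings on days 2 to 27.
3. Keep the Baseline-to-Visit 3 shifts (Tables 14.3.3.2 and 14.3.3.4) as planned, beside the new ones.
4. Reconcile the permissive sentence on unscheduled data in SAP 3.1 with the window-only rule in 3.5, so that the choice is not left until the data are seen. In the same place, say how early-termination records outside a window are labelled.

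The cost is SAP wording and two more outputs from data already collected. For an eye already in the Visit 3 table, the reported grade can only be equal or worse. Early-exit eyes will also enlarge the denominator, so the new tables should show it. The change recovers only findings that were examined: a sign that came and went with no visit stays unseen in either table.
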